3.2 Exclusion criteria

1. Patient unable to or decline to give consent

3.3 Exit criteria

Participation in this study is optional and patients are free to withdraw their participation from this study at any time point during the study process without the need to provide any justification. Withdrawal from this study will not affect participants' future medical treatment.

Patients who have withdrawn their participation are not obligated to continue further follow-up and will not be replaced by new participants in this study. A reasonable sample size has been calculated to account for patient attrition.

Should the reason for withdrawal from the study be due to issues related to either safety or effectiveness of the study device, the investigator shall obtain a new separate consent from the subject, independent of the original study consent, to continue tracking his/her clinical progress/ situation.

3.4 Early termination

The study sponsors reserve the right to terminate the study at any stage should the need arise but will exercise this right only for valid scientific or administrative reasons. The study sponsors, relevant ethics committee and regulatory agencies (if applicable) will be notified in writing at the time of study termination.

3.4.1 Study termination criteria

Study termination refers to the cessation of all tests or follow-up during the progress of a clinical trial program. The main purpose is to protect the rights and interest of clinical subjects, maintain quality assurance testing and to minimize unnecessary economic losses.

Causes for early termination includes (but not limited to) the following:

1. Inability to continue research on grounds of medical and/or ethical considerations
2. Slow enrollment progress such that the study cannot be completed within a reasonable and acceptable time window

3. Decision from Ethics Committee/Board to terminate the study
4. Availability of new information which impacts standard of care (such as product safety/ performance)
5. Boston Scientific Corporation decides to suspend/ halt the development of the study/ test equipment

3.4.2 Study site termination criteria

If a study/ research site (i) is unable to recruit any patients, (ii) has an enrollment rate that is significantly lower than expected (iii) violated the study protocol without due justification or in spite of remedial measures, the study sponsors/ National Heart Centre Singapore (NHCS) reserve the right to remove the study site from the research study.

4. Study design

4.1 Research design

This is a prospective observational multicenter cohort study of all patients with calcified coronary lesions undergoing RA in participating centres across Asia. Patients will be required to provide informed consent for data collection, including follow-up data and uploading of data on a web-based data collection platform (de-identified).

Operators/ institution coordinators will fill up hardcopy or electronic (web-based) forms including patient's baseline demographics, co-morbidities, clinical data, laboratory test results, echocardiography results, coronary angiography findings with subsequent interventions performed as well as follow-up clinical and laboratory results.

Note that while detailed data for individual patients will only be collected if there is informed consent, data from each institution will also be collected for aggregate data regarding procedural volume (eg. total cases with debulking therapy and specifically for ROTABLATOR™). This will give a sense of representativeness of data collected. This screening data will also include the following fields: age, gender, ethnicity, co-morbidities, target vessel, prior revascularization (PCI/CABG), clinical presentation, procedural urgency, angiographic procedural details (RA and PCI) and in-hospital complication and mortality. The use of this retrospective data will require appropriate approval and will only utilize anonymized data. Only in-hospital data will be obtained and no follow up data is required from these controls.

Should these data not be available in any of the participating sites, a minimum baseline demographics, procedural and inpatient outcome data with reasons for non-participation in registry should be provided for records purposes. This shall be accepted as a limitation of the study. Sub-site analysis may be performed in centres with availability of all data in this group of patients to address generalisability of the data collected.

[figure not shown]

Figure 6: Data collection workflow for (i) patients who provide consent vs (ii) patients who declined to provide consent/ unable to give timely consent in view of unexpected demise

4.2 Study stages

4.2.1 Index visit: Within 48 hours of PCI

The following information will be captured during this index visit:

1. Demographics: Age, gender, ethnicity
2. Clinical characteristics: Clinical presentation (STEMI, NSTEMI, UAP, Angina, cardiac arrest), Symptoms (CCS angina score), Co-morbidities (diabetes mellitus, hypertension, hyperlipidemia, atrial fibrillation, smoking status, CKD/ ESRF, prior MI, prior PCI, prior CABG, prior CVA)
3. Laboratory results: full blood count, creatinine, electrolytes, fasting lipids/ glucose, HbA1c, cardiac injury markers i.e troponin T or I, CK, CK-MB)
 - a. If either troponin T or I is to be measured AFTER PCI with rotational atherectomy, a total of 3 sets are recommended at specific time intervals of 0-1 hours (1st set), 4-8 hours (2nd set) and 12-24 hours (3rd set) POST-PCI to ensure uniformity of sample collection across all sites.
 - b. Sites are to also provide the upper limit of normal values for their laboratory assay tests.
4. Medications: prior to PCI, during PCI, on discharge
5. ECGs (a post procedural ECG is required)
6. Echocardiographic data (LVEF)
7. Procedural data: Coronary anatomy (artery dominance, number of diseased vessels, presence of bypass grafts), target lesion (location by artery/grafts, proximal vs mid vs distal, branches (ramus, diagonal, OM, RPDA, graft)), rotational atherectomy (lubricant, burr size, run time, burr speed, number of passes, maximum rotational speed), adjunctive devices (guideliners, guide size, guide shape), PCI (type of PCI performed - POBA vs DEB vs DES, number of stents, pre and post-dilatation, stent overlap),

angiographic outcomes (TIMI flow, angiographic complications) procedural details (fluoroscopic duration, total contrast media)

8. Intravascular imaging data (OCT/ IVUS)
 - a. Sites will also send CDs of their angiograms and intravascular imaging
9. Outcomes data: Primary (residual stenosis in treated segment with TIMI 3 flow without mortality), Secondary (Death, periprocedural MI, complications (coronary perforation, no reflow, slow flow)
10. Primary operator data: ie. Operator initials (further anonymized prior to analysis), Age band, years of interventional cardiology practice, number of procedures. (PCI) performed preceding year (range), approximate number of rotablator performed last year (range)
11. Limited hospital data: number of years with rotablator therapy, approximate number of PCI preceding year, number of rotablator preceding year, availability of orbital atherectomy/ shockwave lithotripsy

Patient will also be asked to sign study consent form (in addition to institutional procedural consent form) to certify agreement to participate in current research study.

4.2.2 Follow-up at 12 months: telephone contact

The following information will be captured during this 12-month follow-up visit: Symptoms (CCS score), medications (antiplatelet therapy, statins, non-statins LDL lowering therapy), outcomes (death, MI, TLR, stent thrombosis, and stroke).

4.3 Data collection of patients excluded from registry

1. Demographics: Age, gender, ethnicity
2. Abbreviated clinical characteristics: Clinical presentation (STEMI, NSTEMI, UAP, Angina, cardiac arrest), Symptoms (CCS score), Co-morbidities (diabetes mellitus, hypertension, hyperlipidemia, atrial fibrillation, smoking status, CKD/ ESRF, prior MI, prior PCI, prior CABG, prior CVA)
3. Abbreviated laboratory results: full blood count, creatinine, fasting lipids, HbA1c, cardiac injury markers i.e troponin T or I, CK, CK-MB)
4. Medications: on discharge
5. Echocardiographic data (LVEF)
6. Procedural data: Coronary anatomy (artery dominance, number of diseased vessels, presence of bypass grafts), target lesion (location by artery/grafts, proximal vs mid vs distal, branches (ramus, diagonal, OM, RPDA, graft)), use of alternative calcium debulking devices, PCI (type of PCI performed - POBA vs DEB vs DES, number of stents, pre and post-dilatation, stent overlap), angiographic outcomes (TIMI flow, angiographic complications) procedural details (fluoroscopic duration, total contrast media)
7. Outcomes data: Primary (residual stenosis in treated segment with TIMI 3 flow without mortality), Secondary (Death, periprocedural MI, complications (coronary perforation, no reflow, slow flow)

5. Medications

All participants are recommended to be initiated on dual antiplatelet therapy (DAPT), one of which must be aspirin and the other is a P2Y12 inhibitor (clopidogrel or ticagrelor) prior to PCI. The duration of DAPT is to be determined by the interventionist. The following recommendations are for physician reference.

(i) Aspirin

If the subject has been taking aspirin daily for ≥ 72 hours prior to PCI, loading of aspirin is not necessary.

If the subject is aspirin naïve or has taken aspirin for less than 72 hours prior to PCI, loading of aspirin prior to PCI is recommended. Dose of aspirin loading is to be determined by the interventionist.

If aspirin is to be loaded, it is recommended to be at least 2-hour prior to PCI.

Patient should be continued on long term aspirin subsequently.

(ii) P2Y12 inhibitors

If the subject has taken P2Y12 inhibitors (e.g. clopidogrel, ticagrelor or prasugrel) ≥ 7 days, loading of P2Y12 is not necessary.

If the subject is P2Y12 inhibitor naïve or has not taken P2Y12 daily for at least 7 days, loading of P2Y12 prior to the PCI is recommended. The dose of P2Y12 is to be determined by the interventionist. Generally, at least 300-600mg of clopidogrel is required for loading, while ticagrelor loading dose is 180mg.

If P2Y12 is to be loaded, it is recommended to be at least 2-hour prior to PCI for both clopidogrel and ticagrelor.

For prasugrel, loading dose of 60mg should only be given once coronary anatomy is known and PCI is planned on table.

The subject should be treated with P2Y12 inhibitor for a minimum duration of 6 months and continued up to at least 12 months if the risk of bleeding is deemed to be low.

(iii) Intraprocedural anticoagulation

The choice of anticoagulation is dependent on operator's discretion to maintain a recommended ACT range of 200-300 seconds.

(iv) Intracoronary medications

The administration of intracoronary glyceryl trinitrate (GTN) is recommended prior to coronary angiography of both left and right coronary artery system.

The use and choice of other intracoronary vasodilators such as CCB, adenosine is left up to operator's discretion/ individual site practice.

(v) Guideline directed medical therapy

Other medications such as statins, ACEi/ ARB, Beta-blockers, calcium antagonists and other drugs use are as per international or local guidelines such as ACC or ESC.

6. Procedure

6.1 Preparation prior to rotational atherectomy

Access planning for an individual patient must balance the need to provide sufficient support for RA and vascular complications that may arise. Generally, a 6 Fr system is adequate to support RA in most cases and is able to accommodate burr sizes up to 1.75mm, thereby permitting either trans-radial or trans-femoral approach. Radial approach has been associated with equivalent procedural success to that of femoral access^{29,30}. As such, radial approach should not be abandoned in patients who have planned RA. In addition, additional support can be enhanced by either using a long sheath, supportive guide catheter or a child-in-mother catheter. In contrary, if a 2.0mm or larger burr size is required or complex bifurcation PCI is planned, a 7Fr or larger catheter may be required, by which a trans-femoral approach may be preferred.

Prior to RA, it is paramount to position a RotaWire across the target lesion with its tip placed as far distally as possible. Primary wiring of target lesion with RotaWire can be challenging and thus initial wiring with either a workhorse or specialty 0.014" coronary guidewire within a micro-exchange catheter or over-the-wire balloon may be easier, subsequently permitting exchange for a RotaWire while concurrently divulging crossing properties of the lesion. In situations whereby the microcatheter is unable to cross the lesion, it is advisable to perform RA with the smallest (1.25mm) burr.

Burr size selection is key to procedural success. As shown in STRATAS and CARAT trial, smaller burrs (with burr: artery ratio < 0.7) have comparable angiographic and procedural success rates to larger burrs but with fewer angiographic complications, less peri-procedural myocardial injury, use of smaller sheaths and guide catheters with consequently lower vascular and bleeding complications^{10,11}. A stepped burr strategy beginning with 1.25 or 1.50 burr with gradual escalation in size up to maximal burr: artery ratio of 0.7 is recommended especially in cases for which micro-exchange catheter will not cross the lesion or lesions with severe angulation, tortuosity or eccentricity.

During the RA process, a flush solution comprising of heparinized saline with RotaGlide lubricant is also recommended to lubricate device motion, prevent sudden decelerations and reduce heat generation. In some instances, vasodilators such as nitroglycerin (50-200 μ g), verapamil (100-200 μ g, up to a total amount of 1.0 – 1.5mg) or diltiazem (0.5-2.5mg, up to 5-10mg) can be incorporated into the flush solution to further reduce risk of microvascular obstruction.

RA involving right coronary artery, left dominant circumflex or use of large burr head (> 2.25mm) are prone to transient microvascular ischemia with consequent risk of bradycardia and conduction blocks. In such situations, prophylactic temporary pacing may be considered. Bradycardia in these situations occur especially during forward grinding spin of the burr and usually recovers after 5 to 60 seconds post cessation of atherectomy or on coughing.

6.2 Rotational atherectomy operational guide

6.2.1 System setup

Plug in console and turn on power switch. Connect the air supply hose to compressed air or nitrogen (minimum of 500 PSI in tank per procedure with 90-110 PSI flowing to console). Connect all 3 Dynaglide foot pedal hoses to the console (green and blue to the back while pink to the front). Then, connect the fiber-optic cables and air -line to the front of the console. Add the RotaGlide lubricant and other adjunctive vasodilators (as indicated) to the 1-liter sterile saline bag and connect it to the ROTABLATOR™ infusion port and pressurize the bag to 150 - 200mmHg.

6.2.2 Procedure preparation

Place both the guide sheath and guidewire sequentially into the target vessel. Advance the guidewire beyond the target lesion and backload burr, stopping just proximal to the sheath. Grasp the proximal tip of the guidewire and thread this end into the hole in the tip of the burr. Continue feeding the wire into the catheter until it appears at the rear of the advancer. Then, grasp the exposed wire and pull it gently until the burr is a few centimeters from the entrance to the guide sheath/ introducer sheath. Thereafter, attach a wireclip Torquer to the end of the guidewire. Ensure that advancer knob is fixed at 2cm from the distal end. Connect the air hose, fiber optic cable and saline infusion port subsequently.

Test the system outside the subject's body with foot pedal activated. Firstly, check the drip from the catheter sheath tip and beneath the advancer. Next, set the burr speed to desired RPM level followed by ensuring the free movement of the advancer knob. Finally, check that the wire is visible out of the advancer with torquer clip attached. Tug on wire during rotating to ensure brake is activated.

6.2.3 Burr positioning and ablation procedure

Under fluoroscopic guidance, gently push the burr through the guide sheath to a point proximally to the target lesion. Check that the burr size is compatible with vessel diameter by contrast injection. Stop the burr in free lumen and when the burr is 1-2cm proximal to the target lesion, retract the advancer knob fully to prevent the burr from darting forward during first activation.

Fully depress the foot pedal to activate the burr. Adjust your foot for optimum position on the foot pedal. Recheck the rotational speed reading to verify that the rotation rate is appropriate for the burr size and lesion type. Generally smaller burrs 1.25mm – 2.0mm burrs require rotational speed of 160,000-180,000 rpm whereas larger burrs of at least 2.15mm require lower rotational speed of 140,000-180,000 rpm.

Slowly push the advancer knob forward and observe progress of burr fluoroscopically. Advance in such a manner such that the burr speed does not decrease lower than beyond 5000 rpm from the unloaded platform speed. This can be assessed by firstly observing the console display initially followed by listening to the corresponding drop in audible pitch. It is recommended to advance and retreat the burr no more than 3cm at a time in a smooth pecking motion. Care should be taken to engage the lesion only minimally when resistance is met. Short individual runs of less than 30 seconds are recommended with total rotational procedure time not to exceed five minutes. In between each interval, small amount of contrast should be injected to assess for burr head position, confirm presence of coronary blood flow and evidence of vascular complications such as

perforation in addition to flushing microparticles to distal ends of vessels. If resistance to motion is encountered, retract the burr and stop treatment immediately. Reassess situation using fluoroscopy. Decision to stop further atherectomy attempts using current burr is dependent on absence of resistance felt throughout the entire length of diseased segments or rotational speed was not significantly decreased during the run.

6.2.4 Burr exchange and procedure completion

When satisfactory RA attempt has been made using the first burr, activate the Dynaglide feature by pressing the button on the foot pedal to exchange burr. When this feature is activated, the RA system will rotate at reduced speed of 60,000 – 90,000 rpm and the guidewire will advance readily when the advancer is withdrawn. The guidewire must be held firmly using the wireclip Torquer whenever the advancer is operated under the Dynaglide mode. With the wireclip Torquer/guidewire combination in docking port, depress the brake defeat button and push forward on the Torquer until it stops, hence locking the brake defeat button in a depressed position. Thereafter, the burr can be withdrawn over the guidewire until a 7cm or larger loop of wire remains. Release the foot pedal then. Thereafter, switch to a larger burr if required or proceed with stent placement if desired treatment outcome has been achieved.

6.3 Intracoronary imaging

Where appropriate, the preferred imaging platform is intravascular ultrasound (IVUS), either with Opticross or Opticross HD. However, the final selection on the use of IVUS or optical coherence tomography (OCT) is subject to operator's discretion based on angiographic findings.

6.4 PCI post rotational atherectomy

For PCI, the preferred type of stent is drug eluting stent (DES), either with SYNERGY or SYNERGY XD per commercial availability. However, the final selection on stent type/ brand is subject to operator's discretion based on clinical indication as well as angiographic findings.

7. Outcomes

7.1 Primary efficacy endpoint

Procedural success defined as < 20% residual stenosis in treated segment without on-table mortality with TIMI 3 flow

7.2 Secondary outcome measures

1. Death (in-hospital and at 1-year follow-up)
2. Periprocedural myocardial infarction (MI) defined as either (within 48 hours of procedure)
 - a. Peak CK-MB $\geq 10x$ ULN OR $\geq 5x$ ULN + new pathologic Q waves in ≥ 2 contiguous leads/ new persistent LBBB² OR
 - b. Peak Troponin T or I $> 5x$ ULN + new pathologic Q waves/ ischemic ECG changes³
3. Complications: Significant coronary perforation defined as (within 48 hours of procedure)
 - a. At least Type II, III or III CS based on Ellis classification⁴

4. Complication: no-reflow or slow flow (within 48 hours of procedure)
5. Procedural time defined as
 - a. Time of guide engagement to removal of guide.

8. Safety assessment

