3.1 Inclusion criteria

Subjects MUST fulfill ALL of the following requirements in order to be eligible for the study:

1. At least 21 years of age of any gender
2. Able to understand and sign an informed consent form
3. Presence of clinical indication for percutaneous coronary intervention (PCI) and/or stent placement
4. Subjects willing to comply with all research and follow-up requirements
5. Angiographic criteria (ONE of the following criteria MUST be met)
 - a. Target lesions visually have at least moderate calcifications*

- b. Target lesion balloon dilatation failure
- c. Inability of devices (microcatheters, balloon, stents or imaging devices) to pass through the target lesion
- d. Intravascular imaging shows severe calcifications*

6. Procedural criteria

- a. All patients treated with RA with or without other forms of debulking therapy

*Moderate calcification is defined as radio-opacities noted only during cardiac cycle prior to contrast injection whereas severe calcification is defined as radio-opacities seen without cardiac motion prior to contrast injection, usually affecting both sides of the arterial lumen¹.

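### The periprocedural MI definition compares the 48-hour peak marker with ULN only, so its CK-MB ≥10× ULN limb could count a presenting infarct as a procedural MI

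*Protocol*

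**What the plan says.** Section 7.2, item 2 (the same text stands in the synopsis) opens with "Periprocedural myocardial infarction (MI) defined as either (within 48 hours of procedure" and lists these ways to qualify:

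- peak CK-MB ≥10× ULN, with no further condition;
- peak CK-MB ≥5× ULN with new Q waves or a new persistent left bundle branch block;
- peak troponin T or I >5× ULN with an ECG sign, worded "new pathologic Q waves/ ischemic ECG changes".

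ULN is the only reference value. No limb asks for a normal, stable or falling value before PCI, or for a rise above it.

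Eligibility is broad. Section 3.1, item 6a takes "All patients treated with RA with or without other forms of debulking therapy", and the only exclusion in section 3.2 is "Patient unable to or decline to give consent". Section 4.2.1 records "Clinical presentation (STEMI, NSTEMI, UAP, Angina, cardiac arrest" among the baseline data, and section 10.7 names acute coronary syndrome as a possible subgroup.

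On sampling, section 4.2.1, item 3a begins "If either troponin T or I is to be measured AFTER PCI with rotational atherectomy" and then recommends three post-PCI troponin sets. It gives no timing for CK-MB and requires no pre-PCI marker. Item 5 reads "ECGs (a post procedural ECG is required". Section 10.5 says that the 48-hour event rates will be estimated with 95% confidence intervals, without restriction by presentation.

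**The concern.** A periprocedural MI rate is meant to describe harm from the procedure. In a patient whose marker is already high because of the infarct that led to PCI, a fixed multiple of ULN cannot separate the presenting event from a new one. The two CK-MB and troponin limbs that need an ECG sign give some protection. The CK-MB ≥10× ULN limb gives none.

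The reported rate could therefore partly reflect how many patients presented with acute MI. A comparison of this endpoint between patients with and without acute coronary syndrome could be distorted by the definition itself. This matters because the registry's hypothesis is that rotational atherectomy is a safe adjunct, and this is one of its few named 48-hour safety outcomes.

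**Working it through.** **Step 1: the written rule applied to one patient.** Take an NSTEMI presenter treated with rotational atherectomy who consents. Sections 3.1 and 3.2 admit this patient if the remaining inclusion criteria are met. Suppose CK-MB is above 10× ULN before PCI, is still above it in a sample after PCI, and the procedure is uneventful. Item 2a is met, no ECG is consulted, and section 10.5 counts the patient as an event. Nothing in sections 4.2.1, 7.2 or 10.5 removes the patient.

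**Step 2: the plan's own interval formula.** The protocol gives no figure for this endpoint. Its Table 1 uses the simple asymptotic interval for another rate (all RA-related complications):

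- n = z²·p(1−p)/(w/2)², with z = 1.95996, p = 0.05 and w = 0.03, gives 810.97, so 811. This reproduces Table 1.

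The same formula serves below. The 811 is not in dispute.

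**Step 3: a yardstick for false positives.** Half-width h = 1.96·√(p(1−p)/n). The smallest whole number of false positives that shifts the estimate by h is h·n, rounded up. The 5% is an assumption. The 2.0% and 7.4% are two MI rates listed in Appendix 1, where MI is not defined.

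| Assumed rate | n | Half-width (points) | False positives |
|---|---|---|---|
| 5% | 1000 | 1.351 | 14 (1.4%) |
| 5% | 800 | 1.510 | 13 (1.6%) |
| 2.0% | 1000 | 0.868 | 9 |
| 7.4% | 1000 | 1.622 | 17 |

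**Step 4: what might occur, on assumptions alone.** Let t be the true procedural MI rate, s the share presenting with STEMI or NSTEMI, and f the share of those who reach CK-MB ≥10× ULN from the presenting infarct. Then the observed rate is t + (1−t)·s·f. The documents give neither s nor f. The ranges s = 10% to 40% and f = 5% to 30% are assumed.

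- t = 2%: 0.98 × 0.10 × 0.05 = 0.0049 up to 0.98 × 0.40 × 0.30 = 0.1176, that is about 5 to 118 false events per 1000 and an observed rate of 2.5% to 13.8%.
- t = 7.4%: 0.926 × 0.10 × 0.05 = 0.0046 up to 0.926 × 0.40 × 0.30 = 0.1111, that is about 5 to 111 per 1000 and an observed rate of 7.9% to 18.5%.

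The low end is smaller than the sampling error and the high end is far larger. The range shows how little is known; it is not an estimate.

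**Step 5: the opposite direction.** Post-PCI troponin is conditional. If a share u of patients is untested, has the same true rate p and is counted as event-free, the rate falls by p·u. At p = 5%, 0.05·u = 0.014 gives u = 28%. About 28% untested would thus cancel a 1.4-point upward shift.

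**The case against.** **The cited sources may cover raised baselines.** Both limbs carry a reference, and the short text could be an abbreviation. But the protocol writes out its own criteria in full, twice, and does not say that it adopts any further rule. The sources are not at hand. The objection lowers certainty about intent and leaves the written rule as it is.

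**An SAP or adjudication document may deal with it.** Such a document could add a baseline rule. The point here, however, is a stated definition that misclassifies, and any later document would have to override it.

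**Presentation is recorded and acute coronary syndrome is a listed subgroup.** This is a real mitigation, because the rate can be shown by presentation. But the subgroups only may be used, and the overall rate would still mix the two kinds of event.

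Some stronger readings are tempting, and the documents do not support them:

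- *The rate will be inflated, and materially.* Neither case mix nor testing rates are given. CK-MB has no post-PCI schedule, and untested patients could pull the rate down.
- *The troponin limb has the same defect.* That holds only if 'new' is read as not covering ischemic ECG changes, which is one possible reading.
- *Pre-PCI markers and ECGs are not collected.* Section 4.2.1 lists the data to be captured and is not the case report form. It makes only the post-procedural ECG compulsory, but it speaks of ECGs in the plural and does not bar pre-PCI values.
- *The primary endpoints, the sample size or the 12-month MACE count are compromised.* Nothing shows this. Whether the 48-hour event enters the 12-month MI and MACE counts in section 8.2 is not stated.

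**Conclusion.** The concern holds as a fault in the written definition. ULN is the only reference, the CK-MB ≥10× ULN limb needs no ECG sign, acute-MI presenters are eligible, and one rate is reported for all. A presenting infarct could therefore be counted as a procedural MI.

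How often this would happen, and whether the net bias is upward or downward, cannot be derived from the documents. The yardstick of 14 patients in 1000 (9 to 17 for assumed rates of 2.0% to 7.4%) says what would move the estimate by one half-width. It does not say that this will occur. One descriptive secondary endpoint is affected. It should be corrected because correction is cheap, but it does not threaten the study's main results.

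**What to change.** 1. In section 7.2 and the synopsis, state that each ULN threshold applies only when that same marker was not elevated before PCI or, if it was not measured before PCI, when the patient did not present with STEMI, NSTEMI or cardiac arrest. Tying the rule to the same marker keeps a patient with raised troponin but normal CK-MB assessable on CK-MB. Write 'new' before the ischemic ECG changes in item 2b.
2. In section 10.5, make the headline rate the one in patients assessable under (1) who have a post-PCI marker recorded. Report two other groups separately, with their numbers: acute-MI presenters or patients with raised baseline markers who are not assessable, and patients with no post-PCI marker. Count neither group as event-free. Also show the rate by presentation.
3. Record whether each marker and each ECG is pre- or post-PCI. The index visit already separates timing for drugs ("Medications: prior to PCI, during PCI, on discharge"), and presentation is already collected. No extra test is mandated.

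The cost is wording in two places, an addition to section 10.5 and a timing label on existing data. The downside is a smaller denominator for this endpoint. At an assumed 5% rate, the half-width grows from 1.35 points at n=1000 to 1.51 at n=800 and 1.61 at n=700. Who is assessable will also depend partly on local testing, which is why the numbers in the separate groups must be shown.
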